9. SUBGROUP ANALYSES

Subgroup analyses for the composite primary endpoints will be performed to assess the consistency of the effect of study treatment across the subgroups. The analysis will be performed with the mITT population. The following baseline variables will be studied (continuous variables will be categorized into terciles):

- age at inclusion (categorized into terciles)
- country
- group of neighbouring countries
- baseline CD4 cell counts (<50 or 50-199 or \geq 200/ μ L)
- baseline CD4 cell counts (<50 or \geq 50/ μ L)
- gender
- transmission group
- ethnic group
- baseline viral load (<100,000, 100,000-500,000, $>$ 500,000)
- Current smoker (no or yes)
- adherence (take medication all the time versus not at all)

If the number of participants is too small (less than 10) within a subgroup, then the subgroup categories may be redefined before locking the database. A forest plot will display confidence intervals across subgroups.

We will use a Cox proportional hazard model to calculate the hazard ratio between BIC and DRV/c of the incidence of the first episode of the composite primary endpoint event in each subpopulation, without adjustments for stratification factors. The heterogeneity of the effect of BIC and DRV/c within subgroups will be assessed by including terms for interactions between treatment group and subgroup variables in a Cox proportional hazard model.

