9.4 Subgroup analyses

Subgroup analyses for the primary endpoint will be done to explore whether estimated treatment effects vary significantly between subcategories of trial participants. The following variables will be assessed: age, gender, transmission group, ethnic group, baseline CD4 (<50, 50-199, ≥200), baseline viral load (<100,000, 100,000-500,000, >500,000), smoker, adherence (>/< 95%) and participating country. Heterogeneity of the treatment effect across subgroups will be assessed by including terms for interactions between treatment and subgroup variables in expanded Cox models. Age will be divided into three groups using tertiles/quartiles.

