3. STUDY METHODS

3.1 GENERAL STUDY DESIGN AND PLAN

LAPTOP study is an international, open-label, randomised, two arm, multicentre trial over 48 weeks to compare two strategies for HIV-1 infected patients with advanced disease.

Eligible patients will be randomised to receive either an integrated inhibitor containing regimen (B (50mg)/F (200mg)/TAF (25mg) [1 pill administered orally once daily for 48 weeks]) or a boosted PI regimen (D (800mg)/C (150mg)/F(200mg)/TAF (10mg) [1 pill administered orally once daily for 48 weeks]). Randomisation is stratified by country and baseline CD4 cell count (<50 cells/ μ L, 50-199 cells/ μ L, or \geq 200 cells/ μ L).

[figure not shown]

Figure 1: Study design

Study participants will be ART-naïve, HIV-1-infected individuals aged 18 or older who have at entry HIV viral load > 1000 copies/ml and at least one of the following: i) have AIDS with any CD4 cell count; ii) have severe bacterial infection (BI) and must have a CD4 cell count < 200/µl within 30 days prior to study entry; iii) are asymptomatic with CD4 cell count < 100/µL within 30 days prior to study entry; iv) are currently receiving treatment for OI. Women who were pregnant or breastfeeding or who declined a contraceptive method at screening were not eligible.

After the screening visit, participants will be seen at baseline, when they initiated c-ART and weeks 4, 8, 12, 24, 36 and 48, as well as a follow-up visit 30 days following the week 48 visit.

At each visit, participants will have routine safety monitoring as well as measurement of plasma HIV-1 RNA viral load, CD4, CD8 cells counts and a deep sequence resistance test. In the event of virological failure, local resistance tests should be performed on the first sample, and participants should discontinue study treatment and receive rescue therapy at the investigators' discretion.

Quality of life (QoL) questionnaire (EuroQoL EQ-5D-3L) and HIV Symptom Index (HIV-SI/SDM) questionnaire will be administrated at each visit from baseline.

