3.2 RANDOMISATION SCHEME AND BLINDING

The randomization list will be generated by an independent statistician not part of the study team. The list will be generated by a centralized computer-generated random list with a permuted block size. He is the only person who know the size of the blocks.

Participants will be randomly assigned, in a 1:1 ratio, to receive a BIC containing regimen or boosted PI containing regimen for 48 weeks, with allocation stratified by country and baseline CD4 cell count (<50 cells/µL, 50-199 cells/µL, or ≥200 cells/µL).

Randomization will be done at the baseline visit (date of the study treatment initiation). This study is open-label; therefore, all investigators, site pharmacists, study nurses and participants will be unmasked and aware of the treatment allocation throughout the study.

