5. GENERAL CONSIDERATIONS

All continuous variables will be summarised using the following descriptive statistics: n (non-missing sample size), mean, standard deviation (SD), 1st quartile, median, 3rd quartile, maximum and minimum. The frequency and percentages (based on the non-missing sample size) of observed levels will be reported for all categorical variables.

The number of participants and the flowchart of the study will be presented. The period of enrolment and the total number of participants screened to be included in the study will be presented. The number of ineligible participants and the total number of randomized participants will be presented.

The number of participants who never receive the study intervention will also be presented by treatment group and those who were included in the full analysis set and the safety analysis set will be presented.

Baseline is considered as the day 1 visit and the baseline data is data collected just before intervention at day 1.

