6.4 STUDY TREATMENT COMPLIANCE

Adherence during the trial will be monitored by subject questioning regarding missed tablets at each visit. Compliance rate for each participant will be estimated by the response of the following item: Thinking about the last week, how often has the subject taken their medication? The response is classified in 5 categories (All the time, Most of the time, About half of the time, Very few times, None). For participants who reported taking their medication "All the time" during the past week, if it is also indicated that they forgot to take their medication at least once since the last visit, they are downgraded to the "Most of the time" category. The compliance rate will be done at each visit. A bar plot will be presented.

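### SAP section 9 lists adherence as a baseline subgroup, but it can only be observed after randomisation, and the split used is ambiguous

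*Combined protocol and SAP*

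**What the plan says.** SAP section 9 introduces its subgroup list with "The following baseline variables will be studied". The last of the eleven entries is "adherence (take medication all the time versus not at all". Every entry gets a hazard ratio per subgroup, a treatment-by-subgroup term in a Cox model and a row in a forest plot.

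Other parts of the SAP bear on this entry:

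- **Baseline** (section 5): "Baseline is considered as the day 1 visit and the baseline data is data collected just before intervention at day 1".
- **Population** (section 3.1): "Study participants will be ART-naïve, HIV-1-infected individuals aged 18 or older".
- **Randomisation** (section 3.2): "Randomization will be done at the baseline visit (date of the study treatment initiation".
- **The adherence item** (section 6.4) asks how often medication was taken in the past week. "The response is classified in 5 categories (All the time, Most of the time, About half of the time, Very few times, None". Anyone in the top level who has also forgotten a dose since the last visit is moved down one level.
- **Timing** (section 3.3 schedule and Table 14): weeks 12, 24, 36 and 48, plus the early termination visit (ETV) if required.
- **Section 10.1.5** analyses the same item descriptively and rules out inference.

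Protocol section 9.4 (v1.5 and v5.0) also lists adherence as a subgroup variable, but with a different cut: "adherence (>/< 95%) and participating country". It does not call the whole list baseline.

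**The concern.** A subgroup hazard ratio keeps the protection of randomisation only if the subgroup is fixed before allocation. Adherence to study drug is not. It can respond to the assigned regimen through pill burden, food requirement or tolerability.

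It can also respond to the outcome. One component of the primary endpoint is an adverse event or IRIS requiring an interruption of more than 5 days, and SAP section 3.1 says participants with virological failure should stop study treatment. Someone who has already failed may report taking nothing in the past week because of that failure. The lowest adherence stratum would then partly consist of people who have had the event.

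What is at stake is interpretation. A forest plot would show an adherence row beside ten rows that are baseline characteristics, with nothing to mark it as different. The row also cannot be programmed uniquely, because the split and the classifying visit are not settled.

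**Working it through.** **1. Plan figures.** The documents give no number for the adherence subgroup. The design figures do reproduce. Events = 4(1.960 + 0.842)² / [ln(0.909/1.606)]² = 96.9, so 97. N = 97 / 0.24 = 404, where 0.24 is the mean of 25% and 23%. The sample size is not in question.

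**2. Timing, from the texts.** Baseline data precede the first dose on day 1. Participants have had no earlier ART, and randomisation and the first dose fall on the same date. No baseline value of adherence to study drug can exist. SAP 6.4 speaks of questioning at each visit, while the schedule and Table 14 start at week 12. On either reading the first answer comes after randomisation. Time at risk for the primary endpoint starts at baseline (SAP 7.1), before any answer.

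**3. The split.** The item has five levels. Read literally, the split uses the top level and, presumably, None. Most, about half and very few are left unassigned: 5 − 2 = 3 levels. No level is actually named as the split's lower group. With four scheduled visits, no visit or summary across visits is given. A five-level answer does not yield a percentage, so the protocol's 95% cut cannot be recovered from it.

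**4. Size of the lowest level (assumption; the documents give no distribution).** If 0.5% to 5% of 440 answer None, the level holds 440 × 0.005 = 2 to 440 × 0.05 = 22 participants. At a 24% failure risk that is 0.5 to 5 events.

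**5. Events before the first scheduled answer (assumption: constant hazard).** PI arm: 1 − 0.75^(12/48) = 6.9%, or 15.3 of 220. INI arm: 1 − 0.77^(12/48) = 6.3%, or 13.9 of 220. Together that is 29.2, against 220 × 0.25 + 220 × 0.23 = 105.6 expected events, or 28%. This is only a rough guide, because insufficient virological response is assessed only at weeks 12 and 48 and failures will not be spread evenly.

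**6. Can the analysis mislead when nothing is there?** Illustrative simulation: 220 per arm, no treatment effect, no true interaction, mean hazard corresponding to 25% risk, and a frailty that drives both failure and a two-level adherence variable; 1,500 runs per scenario. The true hazard ratio is 1 throughout.

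| How the arm affects adherence | Rejection at 5% | Ratio of stratum HRs | Stratum HRs |
|---|---|---|---|
| Not at all | 4% | 1.00 | 1.01, 1.01 |
| Shifts its level only | 5% to 7% | 0.91 to 0.94 | 1.14 to 1.30 |
| Changes how frailty drives it | 13% to 33% | 0.56 to 2.1 | 0.58 to 1.51 |

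The simulation leaves out the further route in which failure itself lowers the adherence answer.

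**The case against.** The strongest reply is that little depends on this row. The SAP calls its subgroup analyses exploratory, adherence is one of eleven entries, and the primary Cox model does not use it. That stands, and it limits the weight of the point.

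Four stronger claims are tempting, and the documents do not carry them.

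- **That the interaction test is biased.** This is not established. The simulation is near nominal when the arm does not affect adherence or only shifts its level. Inflation needs a further assumption about how the arm alters the link between frailty and adherence.
- **That anyone failing before week 12 has no adherence value.** The item can be asked at the ETV, and SAP 5.3 uses ETV values to fill the nearest missing visit. Participants who stop drug are encouraged to attend to week 48. Absence of a value is secure only for early deaths and for early losses without an ETV. Where an early failure does have a value, it may have been recorded after the event, which is the other half of the problem.
- **That three levels are certainly dropped.** The wording may be a slip for anything short of full adherence. The downgrade rule in SAP 6.4 fits that reading. It would close the coverage gap, but not the timing problem.
- **That one level will fall below 10 participants.** No response distribution is given, and section 9 already allows categories with fewer than 10 to be redefined before database lock. That rule deals with sparseness, not with timing.

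It is also fair that adherence is named in protocol 9.4, so deleting it from the SAP alone would create a new discrepancy.

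**Conclusion.** The point holds. It rests on the SAP's own definition of baseline, the ART-naive population, randomisation on the first treatment day and the visit schedule; none of these needs an assumption. The adherence stratum hazard ratios and interaction are open to bias and should not be displayed as equivalent to the baseline subgroups. Section 9 also conflicts with section 10.1.5, which bars inference on the same item.

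How large the bias would be, and in which direction, cannot be derived from the documents. The simulated 4% to 33% rejection range shows what is possible under stated assumptions and is not a forecast for this trial. The split is ambiguous rather than demonstrably wrong, but it needs settling along with the classifying visit and the protocol's 95% cut. The change should be made; the primary non-inferiority conclusion does not depend on it.

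**What to change.** **Preferred.** Remove adherence from the SAP section 9 subgroup list, interaction tests and forest plot. Keep it descriptive in section 10.1.5. Record the departure from protocol 9.4 under protocol 9.8, which requires deviations from the statistical analysis plan to be recorded.

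**If it is retained.** Report it apart from the baseline subgroups and label it non-randomised and exploratory. Split full adherence against any lower level, so that all five levels are assigned. Classify by the week-12 answer. Start follow-up after the week-12 visit among participants still event-free, and count week-12 insufficient-response failures as occurring before the landmark. State that this replaces the 95% cut. Under the constant-hazard assumption this sets aside about 29 of 105.6 expected events.

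**Cost.** One SAP entry and a deviation note; SAP 5.1 allows updating before sign-off. One exploratory subgroup is lost, and it would have told little. With 97 events divided in proportion q to 1 − q, the standard error of the log ratio of hazard ratios is √[4/(97q) + 4/(97(1 − q))]. That gives 0.406 at an even split and 0.508 at 80:20. Power to detect a ratio of 2 is then about 40% and 28%.

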10. OTHER ANALYSES

10.1 OTHER SECONDARY ENDPOINTS

10.1.1 ART and/or opportunistic infection/bacterial infection treatment changes and/or dose modifications due to toxicities and/or DDI with ART, and/or IRIS through week 48

Endpoint

The endpoint is the proportion of patients with ART treatment changes and/or dose modifications due to toxicities and/or DDI with ART, and/or IRIS through week 48.

Descriptive statistics and graphical representation

The analyses will be performed with the mITT population and DPS1. Data will be summarised with the number and percentage of participants with ART or OI/BI treatment changes or dose modifications due to toxicities and DDI and IRIS through week 48. The list of patients with the event of interest will be reported in a table, including the previous and the current treatment, start date, end date and the reason for change.

Statistical methodology

The percentage of patients with ART n treatment changes due to toxicities and/or DDI with ART, and/or IRIS will be estimated by the number of patients with the event of interest divided by the total number patients in ITT population. The effect of study treatment on the proportion of patients with ART treatment changes due to toxicities and/or DDI with ART, and/or IRIS at week 48 will be assessed using a logistic regression model with treatment group and adjustments for stratification factor (country/group of neighbouring countries and baseline CD4 cell counts (<50 or \geq 50/ μ L)). An adjusted odds ratio (OR) and the associated 95% Confidence Interval (CI) will be calculated. Similar analyses will also be performed separately for each component (toxicities, DDI, and IRIS). If no events were observed in a group, the comparison will be made using Fisher's exact test.

10.1.2 Health care resource use, through week 48

Endpoint

The endpoint is the proportion of patients with health care resource use, through week 48.

Descriptive statistics and graphical representation

The analyses will be performed with the mITT population and DPS1. Data will be summarised with the number and percentage of participants with health care resource use, including total inpatient days and emergency room visits through week 48.

Statistical methodology

The percentage of patients with health care resource use, including total inpatient days and emergency room visits will be estimated by the number of patients with the event of interest divided by the total number patients in ITT population.

The effect of study treatment on the proportion of patients with health care resource use, including total inpatient days and emergency room visits at week 48 will be assessed using a logistic regression model with treatment group and adjustments for stratification factor (country/group of neighbouring countries and baseline CD4 cell counts (<50 or $\geq 50/\mu\text{L}$)). An adjusted odds ratio (OR) and the associated 95% Confidence Interval (CI) will be calculated.

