Darunavir as a component of D/C/F/TAF fix-dose combination can cause transient and usually asymptomatic elevations in serum aminotransferase levels and has been linked to rare instances of clinically apparent, acute liver injury. No dose adjustment of D/C/F/TAF is required in patients with mild or moderate (Child-Pugh Class A/B) hepatic impairment or in patients with estimated glomerular filtration rate according to the Cockcroft-Gault formula (eGFR_{CG}) ≥ 30 mL/min. The most frequent adverse reactions reported were diarrhea, nausea, fatigue, headache, and rash. Darunavir contains a sulphonamide moiety and should be used with caution in patients with a known sulphonamide allergy. Co-administration of D/C/F/TAF and medicinal products primarily metabolised by CYP3A may result in increased systemic exposure to such medicinal products, which could increase or prolong their therapeutic effect and adverse reactions.

The overall benefit-risk assessment for B/F/TAF and D/C/F/TAF is favourable at this time.

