2.4.2 Secondary endpoints/outcomes

- Proportion of patients with HIV-RNA viral load < 50 copies/mL at week 24, 36, 48
- HIV-1 drug resistance at confirmed virological failure (genotype)
- Time to reach CD4 count > 200/ μ L (first measurement)
- Proportion of patients with CD4 cell count < 200 μ L and < 350 μ L at week 4, 8, 12, 24, 36, 48
- CD4/CD8 ratio at week 4, 8, 12, 24, 36, 48
- Incidence of IRIS in the two arms through week 48
- Incidence and duration of hospitalisation, rate of relapse of specific OI/BI through week 48
- Safety and tolerability, measured by Grade 2, 3 and 4 signs and symptoms and laboratory toxicities through week 48
- ART and OI/BI treatment changes and dose modifications due to toxicities and DDI with ART, and IRIS through week 48
- Health care resource use, including total inpatient days and emergency room visits through week 48
- QOL and functional status outcomes, including overall self-reported QOL and functional status compared in the two groups at week 48
- Discontinuation or modification of study medication due to insufficient virological response, resistance mutations at baseline, or resistance mutation development before week 48

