The incidence of hospitalisation will be estimated by the Kaplan-Meier estimate. The Log-rank test will be used to compare the two survival functions. The duration of hospitalisation will be estimated by the cumulative days of hospitalisation during the course of study and will be compared between the 2 groups by using the Mann-Whitney test. The rate of relapse/recurrence will be estimated by the number of patients with relapse/recurrence divided by the total number patients in ITT population. Fisher's exact test will be used to compare the 2 groups.

The frequency of each Grade 2, 3 or 4 AEs, laboratory toxicities, and ART and OI/BI treatment changes and dose modifications due to toxicities and IRIS will be described and compared by group. Fisher's exact test will be used to compare the 2 groups.

The proportion of patients with health care resource use, and emergency room visits will be compared in the two groups with Fisher's exact test. The total inpatient days will be estimated by the cumulative inpatient days during the course of study and will be compared between the 2 groups by using the Mann-Whitney test.

To assess the impact of study treatment on the evolution of QOL at week 48, we will use multiple imputation approach to replace missing values. We will compare the treatment effect on QOL on each of the 5 datasets generated, including the imputed values, and the results will be combined with Rubin's rules. A generalized estimating equation (GEE) model will be used.

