Mean (95% CI) difference from baseline to week 48			

TABLE 7: SAFETY

	Integrase inhibitor (N=XXX) Person-Year (P-Y): XXX.X			Protease inhibitor (N=XXX) Person-Year (P-Y): XXX.X			P-value
	N of events	N of pts (%)	Incidence rate/100 p-y	N of events	N of pts (%)	Incidence rate/100 p-y	
Any adverse events (AEs : grade ≥2)							
Grade 2							
Grade 3							
Grade 4							
Grade unknown							
Grade 3 or 4 AE							
Drug related AEs							
Drug related grade 3/4 AEs							
dress syndrom (rash)							
IRIS							
IRIS-Kaposis sarcoma							
PML-IRIS requiring hospitalisation							
progressive rash							
transaminitis							
worsening symptoms of Progressive multifocal leukoencephalopathy							
....							
....							
AE leading to the study drugs interruption							
Serious adverse events (SAE)							
Laboratory toxicities							
Death							

TABLE 8. OTHER SECONDARY ENDPOINTS

	Integrase Inhibitor	Protease Inhibitor	Adjusted OR	P-value
	N=XXX	N=XXX	(95% CI)	
Percentage of patients with HIV drug resistance mutations among those with virological failure				
Proportion of patients with ART treatment changes due to toxicities and/or DDI with ART, and/or IRIS through week 48 - due to toxicities - due to DDI - due to IRIS				
Proportion of patients with with health care resource use, including total inpatient days and emergency room visits through week 48				
Proportion of patients with discontinuation or modification of study medication due to insufficient virological response or resistance mutations development before week 48 - for insufficient virological response - resistance mutations development				
Proportion of patients for whom there is a difference in the list of mutations (Stanford list last available version) detected by deep sequencing compared with those detected by population sequencing				

TABLE 9: EVOLUTION OF QUALITY OF LIFE (HEALTH STATUS SCORE) AND HIV SYMPTOMS INDEX

Week	QOL : health status score			HIV Symptoms index score		
	Integrase Inhibitor	Protease Inhibitor	P-value between groups	Integrase Inhibitor	Protease Inhibitor	P-value between groups
	Mean (SD)	Mean (SD)		Mean (SD)	Mean (SD)	
0						
4						
8						
12						
24						
36						
48						
Mean (SD) from baseline to W4						
Mean (SD) from baseline to W8						
Mean (SD) from baseline to W12						
Mean (SD) from baseline to W24						
Mean (SD) from baseline to W36						
Mean (SD) from baseline to W48						

TABLE 10: QUALITY OF LIFE DIMENSIONS: MOBILITY AND SELF- CARE

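### SAP 10.1.1 and Table 8 compare the arms on ART changes only, although the secondary endpoint they serve also covers OI/BI treatment changes and dose modifications

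*Combined protocol and SAP*

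**What the plan says.** Protocol 2.4.2 lists the secondary endpoint as "ART and OI/BI treatment changes and dose modifications due to toxicities and DDI with ART, and IRIS through week 48", and SAP 2.2.2 repeats it. Protocol 9.3.3 gives the analysis: "ART and OI/BI treatment changes and dose modifications due to toxicities and IRIS will be described and compared by group", with Fisher's exact test. That sentence names toxicities and IRIS as reasons but not DDI. Protocol v1.5 and v5.0 agree on both points, and the summaries of changes record no narrowing to ART.

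SAP 10.1.1 starts from the full scope in its heading: "ART and/or opportunistic infection/bacterial infection treatment changes and/or dose modifications due to toxicities and/or DDI with ART, and/or IRIS through week 48". Its endpoint sentence then reads "The endpoint is the proportion of patients with ART treatment changes and/or dose modifications due to toxicities and/or DDI with ART", continuing to IRIS, with no mention of OI/BI treatment. The descriptive paragraph returns to the full scope ("number and percentage of participants with ART or OI/BI treatment changes or dose modifications due to toxicities and DDI and IRIS through week 48") and adds a listing of affected patients with previous and current treatment, dates and reason. The inferential sentence is narrow again: "The effect of study treatment on the proportion of patients with ART treatment changes due to toxicities and/or DDI with ART", and so on to IRIS, analysed by adjusted logistic regression. The planned component analyses split by reason, not by which treatment was changed. The Table 8 row is "Proportion of patients with ART treatment changes due to toxicities and/or DDI with ART, and/or IRIS through week 48", with sub-rows for the three reasons.

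**The concern.** The SAP departs from the protocol and from its own endpoint list without giving a reason. Two things are lost from the between-arm comparison: changes to infection treatment, and dose modifications of any treatment.

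The first loss matters more, because protocol 1.2.2 describes an effect of the boosted regimen on companion drugs: "Co-administration of D/C/F/TAF and medicinal products primarily metabolised by CYP3A may result in increased systemic exposure to such medicinal products". The same section names fewer DDIs as a benefit of the unboosted regimen, and patients under treatment for an OI are eligible (protocol 5.1). Changes to infection treatment are one place where such an effect could appear. The trial could then report an odds ratio near 1 for treatment changes when that odds ratio never counted them. In an open-label trial, a comparison added after the results are known would be post hoc.

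**Working it through.** The point rests on the text. The plan states no figure for this endpoint, so there is none to reproduce.

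**Step 1. Scope in each place.**

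| Place | ART changes | OI/BI changes | Dose modifications | Reasons | Use |
|---|---|---|---|---|---|
| Protocol 2.4.2, SAP 2.2.2 | yes | yes | yes | toxicity, DDI, IRIS | definition |
| Protocol 9.3.3 | yes | yes | yes | toxicity, IRIS | compared by arm |
| SAP 10.1.1 heading | yes | yes | yes | all three | title |
| SAP 10.1.1 endpoint sentence | yes | no | yes | all three | definition |
| SAP 10.1.1 summary | yes | yes | yes | all three | descriptive |
| SAP 10.1.1 percentage and model | yes | no | no | all three | compared by arm |
| SAP Table 8 | yes | no | no | all three | compared by arm |

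Every line that produces a between-arm result in the SAP is narrower than the definition.

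**Step 2. Is the gap filled elsewhere?** SAP 7.2.10 compares relapse or recurrence of infection, not change of its treatment. SAP 8 compares adverse events. SAP 10.1.4 concerns study medication stopped or modified for virological reasons. None compares OI/BI treatment changes.

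**Step 3. Follow one patient.** The infection drug is changed because of a DDI and ART continues. The patient is counted in the 10.1.1 summary. In the logistic model and in Table 8 the same patient is a non-event.

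**Step 4. Illustration of size (all rates assumed).** Inputs: 220 per arm (SAP 4) and two-sided 5% (protocol 9.3.3). Let a be the ART-change rate, taken as equal in both arms, and b the OI/BI-change rate. With independent events, the rate of either change is 1 − (1 − a)(1 − b). Power for an unadjusted comparison is Φ[(|p1 − p2| − 1.96·SE0)/SE1], with SE0 = √(2p̄(1 − p̄)/220) and SE1 = √([p1(1 − p1) + p2(1 − p2)]/220).

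Example, b = 5% vs 15%: p̄ = 0.10, SE0 = 0.0286, SE1 = 0.0282, (0.10 − 0.0561)/0.0282 = 1.56, so power is 0.94. For either change with a = 5%: 1 − 0.95 × 0.95 = 9.75% and 1 − 0.95 × 0.85 = 19.25%, power 0.81.

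| OI/BI changes, BIC vs DRV/c | ART-only test | OI/BI alone | Either, a = 5% | Either, a = 10% |
|---|---|---|---|---|
| 5% vs 10% | 5% | 51% | 33% | 24% |
| 5% vs 15% | 5% | 94% | 81% | 67% |
| 10% vs 20% | 5% | 84% | 72% | 61% |

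The ART-only column follows directly from setting the ART rates equal: the test then rejects at its type I error rate. The last two columns show that modelling only the combined event would dilute an OI/BI difference.

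**The case against.** There are several fair points in favour of the SAP.

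- A reader might infer that a secondary objective on interactions and toxicity goes untested. The documents do not support that. The secondary objectives (protocol 2.2, SAP 2.1.2) name tolerability but not interactions, and this is one of 13 secondary endpoints in SAP 2.2.2. SAP 8 compares adverse events and laboratory toxicities between arms, and 10.1.1 still tests DDI as a reason for changing ART.
- A reader might infer that OI/BI changes have vanished. They have not: the summary and listing would show an imbalance. What is missing is the inferential comparison and its table rows.
- Protocol 9.3.3 does not name DDI, so the protocol's analysis section never promised a test of DDI-driven OI/BI changes. For ART, SAP 10.1.1 goes further than the protocol does. The DDI part of the point rests on the endpoint lists alone.
- A reader might infer that a real DDI difference would be missed. That is inference. The CYP3A statement is general, and nothing says that the drugs used for these infections are affected or that an interaction would be handled by changing them. Protocol 5.2 excludes patients on contraindicated or disallowed drugs and those needing rifampicin or rifabutin, and 7.6 asks that interacting drugs be reviewed or avoided. Some patients enter on a low CD4 count without symptoms and may have no infection treatment to change.

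All of this limits the consequence. None of it supplies the comparison of OI/BI changes for toxicity and IRIS that protocol 9.3.3 promises, or explains why it was left out.

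**Conclusion.** The concern holds as a mismatch between the defined secondary endpoint and its planned comparison. Followed as written, the SAP gives no between-arm result for OI/BI treatment changes or for dose modifications. The finding needs no assumption about rates or mechanism; it follows from the wording of protocol 2.4.2 and 9.3.3 and SAP 2.2.2, 10.1.1 and Table 8.

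Its practical size is unknown. The power figures assume equal ART-change rates, independent events, 220 per arm and an unadjusted test, and they show only what the ART-only comparison cannot see. The primary endpoint is unaffected. The change should be made, but the trial's main conclusion does not depend on it.

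**What to change.** Before the SAP is signed off and the database locked:

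1. In SAP 10.1.1, define the event as any change or dose modification of ART or OI/BI treatment due to toxicity, DDI with ART, or IRIS.
2. Fit the planned adjusted logistic model to three outcomes: either treatment, ART alone, and OI/BI alone. Analyse each by reason as well, with Fisher's exact test where a group has no events, as already planned.
3. Add the matching rows to Table 8.
4. Add DDI to the comparison sentence in protocol 9.3.3 so that it agrees with 2.4.2.

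If the restriction to ART is intended, record it as a deviation from the protocol and give the reason.

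The cost is wording, a few more secondary comparisons and some table rows. Concomitant medication is scheduled at every visit (protocol Appendix 1), and the listing in 10.1.1 already calls for the treatments, dates and reasons. The SAP is at v0.3, and SAP 5.1 provides for updating before final approval.
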